### Follow-up from Sleep study results:

As discussed above, we anticipate that approximately 30-40% of our participants will have an abnormal apnea hypopnea index (AHI), requiring some type of follow-up. We have worked with Drs. [name], [name] and [name], our primary pediatric sleep pulmonologists to develop a post-study follow-up algorithm. Of note, [name] is currently working with Kaiser to verify the accuracy of the results from the WatchPAT device as compared to inpatient polysomnograms in children younger than 12, and is very familiar with this device, it's output and limitations. Our youth fall into a grey zone in terms of what is an abnormal sleep study, as pediatric criteria are defined for less than 12, and adult for 18 or older. The international accepted clinical criteria are listed below, as well as the American Academy of Sleep Medicine's recommendations of how to handle age 12-17:

#### Pediatrics:

Mild OSA	Moderate OSA	Severe OSA
1 to 4.9	5 to 9.9	>10

#### Adults

Mild OSA	Moderate OSA	Severe OSA
5 to 14.9 + symptoms	15-30	>30

### A. Ages for Which Pediatric Respiratory Scoring Rules Apply

[figure not shown]
1. Criteria for respiratory events during sleep for infants and children can be used for children <18 years, but an individual sleep specialist can choose to score children ≥13 years using adult criteria.N1 RECOMMENDED

**Note 1.** Several studies suggest that the apnea hypopnea index (AHI) will be higher in adolescent patients when using pediatric compared to the adult rules presented in the 2007 version of the AASM scoring manual. As [adult hypopnea rule 1A](#) and pediatric hypopnea rules are similar, there may now be less difference in the AHI when using adult versus pediatric rules.

[figure not shown]
Copyright © 2014 by the American Academy of Sleep Medicine. All Rights Reserved. Scoring Manual Version 2.1

Since the recommendations are not concrete for the 12-17 year old range, we sought to follow what is being done in clinical practice at Children's Hospital Colorado sleep clinics, were a patient to have an inpatient polysomnogram. Sleep studies are read within 5 business days, and we will adhere to this same turnaround timeline. In terms of interpretation, currently, the pediatric guidelines are being applied for the 12-17 year old age group but 2 is considered normal in this age, and thus our post-study for the 12-17 year olds will follow this, and are shown below. Approximately half of the participants have a patient relationship with the PI [name], and thus she can order F/U evaluation if needed, and if not, [name] will request the follow-up be arranged by the primary care provider. We have 2 algorithms by age.

### For participants 12-17 years of age:

### For participants ≥18 years of age:

## PARTICIPANT RECRUITMENT/CONSENT/PAYMENT

### 1. Participant Recruitment Plan

Participants will be recruited from pediatric endocrine, PCOS, Lifestyle, adolescent and gynecology clinics, and from the community. We receive 4-8 new PCOS referrals a month, showing the feasibility of recruiting the required participants. Further, we enrolled >100 obese girls in studies in the last 60 months. The PI and Co-I's have a treatment relationship with girls from clinic or participants can call from study

advertisements. Protected health information will only be accessible by study investigators. The initial patient contact will be made by personnel who have a treatment relationship with the participant.

## **2. Informed Consent Plan**

Appropriately qualified and informed personnel who have completed the COMIRB and HIPAA course requirements will fully explain the study protocol and consent form to the participant and guardian verbally in the language they understand. The explanation will be conducted in a quiet environment with adequate time given for the participant and guardian to review the study procedure before the commencement of the study. Asking the participant to explain the study in their own words will assess the participant's understanding. If non-English speaking participants are enrolled in the study, the investigators will adhere to Section 10C of the COMIRB Instructions for Clinical Investigators regarding the consent of these participants. The consent form will also be translated into Spanish. The qualified personnel mentioned above will then obtain written consent from the guardian and assent from the participant, co-signed on the consent form, or in participants who are 18 years or older, direct consent. The participant and guardian will be provided a copy of the consent form for better understanding and record purposes.

## **3. Special Consent/Assent Plan**

Consent will be obtained from all participants in the study. Following explanation, all participants below 18 years old will co-sign the consent form in addition to the parents signing the consent form. All participants age 18 or older will sign the standard consent form.

## **4. Participant Compensation, Incentives and Rewards**

Participants will be compensated with Target gift cards for completion of each study visit. The initial visit consisting of informed consent, lab draw, and abdominal ultrasound fibroscan will result in a \$50 gift card. Each of the 2 MRI's (Visits 2 and 4) will be \$50 each. Each of the two overnight visits (Visits 3 and 5) will be \$150 each. In an effort to maintain participant retention and completion of the study, the participants will be rewarded an additional \$50 if they complete all study visits 1-5. Compensation for all completed visits will total \$500.

## **D. Description, Risks and Justification of Procedures and Data Collection Tools:**

**Please note:** with the emergence of COVID-19 we must follow hospital policies for screening hospital patients and visitors. This may include testing for COVID-19. This may involve a nasal swab, and the risks of this are discomfort and potentially bleeding from nose. To limit participant time in our clinics, portions of study visits may be done virtually (phone or Telehealth).

### **1. Blood Sampling**

**Description:** Blood will be drawn for Complete Blood Count (CBC), HbA1c, total and free testosterone, and sex hormone binding globulin. If participants have not had a full evaluation for oligomenorrhea, Prolactin, DHEAS, LH, FSH, TSH, total T4 or 17-OH progesterone may be drawn.

**Risk:** Minimal. Risk of pain, bruising at site of blood draw, excessive amount of blood.

**Minimizing Risk:** Certain studies at our institution draw over 7ml/kg in 6 weeks, or up to 7 ml/kg in a single draw, but include iron supplementation. Otherwise, the routine guidelines in our Pediatric CTRC are 2.5ml/kg for a single draw and no more than 5 ml/kg over a 4 week period. Our baseline visit will include 11.5 ml of blood (HbA1c, Hb, Cr, AST, ALT) and 25.5 ml of blood for PCOS patients (additional draw for T4, TSH, prolactin, LH, FSH, 17OH progesterone and DHEAS). The OSTT visit includes up to 300 ml of blood which will occur within 4 weeks of the initial visit. Thus, our OSTT visit is within the NIH Clinical Center guidelines of 9 ml/kg in 6-8 weeks and within Children's Hospital Colorado's institutional guidelines of 5 ml/kg. In addition, by study design, participants are screened by our baseline CBC and excluded if anemic, further increasing the safety of the study regarding blood draws. We will use a minimum weight cutoff of 38 kg to remain below the most conservative pediatric CTRC blood drawing guidelines. This screening also helps to increase the safety of the blood draw. In addition, the blood planned to be frozen and held could also be omitted if needed to reduce blood volume for a particular participant. Finally, our CTRC has a system to track other studies participants might enroll in, and we ask

during our consent process if the participant has been involved in any other studies in the past 6 weeks to avoid excessive blood drawing.

*Justification:* Screening laboratory measurements are necessary to assure that patients meet inclusion/exclusion criteria before any further study is completed. A CBC is necessary as a screening lab, to rule out anemia. A hemoglobin A1c can be used to rule out diabetes. Hormone levels of free and total testosterone, and sex hormone binding globulin are needed to categorize patients as having PCOS, and prolactin, DHEAS, LH, FSH, TSH, total T4 or 17-OH progesterone to rule out other causes of oligomenorrhea, if not done previously.

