Details of Stable Glycerol Isotope Tracer studies with an OSTT: Participants will fast overnight, and drink 3 doses of D2O three times during the night with doses at 6-8PM, 10-11 PM and 2-3 AM as described previously in obese youth. The total D2O to be given (3 mL per kg of body water) is designed to raise body deuterium levels to 0.3% and was administered in three doses to maintain the steady state until the end of the study. Serum samples will be collected in the morning before the glycerol, and then throughout the OSTT, and VLDL TG separated and then enrichment in palmitate measured. By evaluating the incorporation of the D2O into palmitate, we will be able to assess the DNL expressed as a percentage of DNL. We will also measure the rate of gluconeogenesis by measuring the enrichment in serial plasma glucose samples.

The following morning at approximately 7:00AM, a 50 mg/kg of an oral C-glycerol tracer will be consumed mixed with water. Blood samples will be collected and at approximately 10AM, participants will consume a 75 gram glucose load with an additional 25 grams of fructose to stimulate hepatic de novo lipogenesis. Analysis of serum glucose isotopomers will be performed by our collaborator [name] at UT Southwestern, using NMR isotopomer analysis and pathway modeling software. Lipolysis will be modeled using FFA concentrations and whole body IR by a time modified version of the Matsuda model.

Using a metabolic cart and hood, resting VO2 (ml/kg/min) and VCO2 (ml/kg/min) measurements (REE) will be collected the morning of the OSTT prior to the start of the OSTT, and two more times during the OSTT. This is required to determine what portion of ingested carbohydrates are subject to oxidative and non-oxidative glucose disposal.

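### The baseline CBC is relied on as a blood-draw safeguard, but no listed test rechecks haemoglobin before the second OSTT draw of up to 300 mL (minor, participant safety only)

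*Combined protocol and SAP*

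**What the plan says.** Section III.D.1 (Blood Sampling) presents the screening CBC as one of several protections: "participants are screened by our baseline CBC and excluded if anemic, further increasing the safety of the study regarding blood draws". Its justification paragraph describes the test's role: "A CBC is necessary as a screening lab, to rule out anemia". The screening lab table under Visit 1 lists haemoglobin and excludes anaemic girls. The exclusion criteria set the limit at 11; the printed unit is mg/dL, taken here as g/dL.

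On volume, the same section says: "The OSTT visit includes up to 300 ml of blood which will occur within 4 weeks of the initial visit". It gives the routine limits of the pediatric research unit as "2.5ml/kg for a single draw and no more than 5 ml/kg over a 4 week period" and also describes the OSTT visit as "within the NIH Clinical Center guidelines of 9 ml/kg in 6-8 weeks". It adds two further protections: "We will use a minimum weight cutoff of 38 kg to remain below the most conservative pediatric CTRC blood drawing guidelines", and "the blood planned to be frozen and held could also be omitted if needed to reduce blood volume for a particular participant". Iron supplementation is mentioned only for other studies at the institution that draw larger volumes.

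Visit 5 is defined by reference to Visit 3, so the OSTT draw is made twice. The Timeline and the note closing the Visit 3 description put about 4 weeks of washout and then 4 weeks of the second treatment between the two.

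**The concern.** The safeguard is applied once, before either large draw. The first draw is itself a reason why haemoglobin might be lower at the second. The Blood Sampling section discusses one OSTT visit and does not consider the two together.

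A girl who enters just above the trial's limit could be below it by Visit 5, and no listed result would show this before up to 300 mL more is taken. Participants may be as young as 12. What is at stake is the safety of individual participants, not the estimate of the treatment effect.

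**Working it through.** **1. Is haemoglobin listed after screening?**
- Visit 1 lab table and Blood Sampling section: yes, at screening.
- Study Calendar: only an unspecified blood draw at Visits 3 and 5.
- Visit 3 description, which also governs Visit 5: baseline metabolic bloods on the OSTT morning, not itemised.
- OSTT Labs table under Visit 5: tracer samples, glucose, insulin, FFA, glycerol, hormones, CRP, metabolomics, a genetic sample and stored blood; no CBC or haemoglobin.
- Sections III.A and VII: HbA1c appears, but that is not a haemoglobin concentration.
- Section VI.C (Participant Discontinuation Criteria): the haemoglobin rule concerns screening labs.

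**2. Spacing and volume.** Visit 3 to Visit 5: about 4 + 4 = 8 weeks. Two draws: 2 × 300 = 600 mL at most.

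**3. Does the weight cutoff do the same job?** It bounds volume and does not measure haemoglobin. Nor does it deliver the volume limit. With mL/kg = volume / weight and minimum weight = volume / limit:
- one OSTT at the cutoff: 300 / 38 = 7.9 mL/kg;
- weight needed for 5 mL/kg: 300 / 5 = 60 kg;
- weight needed for 2.5 mL/kg, if the visit counts as a single draw: 300 / 2.5 = 120 kg;
- weight needed for 9 mL/kg, if both draws fall within 8 weeks: 600 / 9 = 66.7 kg.

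A figure near 38 kg is recovered only from the 9 mL/kg limit with one OSTT plus 11.5 + 25.5 = 37 mL at screening: 337 / 9 = 37.4 kg. This reads the 25.5 mL as additional, which the text leaves unclear.

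**4. Could haemoglobin fall below 11 g/dL by Visit 5?** The documents give neither blood volume nor recovery, so this is illustration only. Assume a blood volume of 65–70 mL/kg at 60 kg and 45–70 mL/kg at 100 kg, and let a fraction f (0 to 1) of the loss be recovered by Visit 5. The fractional loss is L = 300 / (weight × mL/kg): 7.1–7.7% at 60 kg and 4.3–6.7% at 100 kg. Entry values from 11.0 up to 11 / (1 − L(1 − f)) would then be below 11 at Visit 5:

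| Recovered | 60 kg | 100 kg |
|---|---|---|
| 0% | 11.8–11.9 | 11.5–11.8 |
| 50% | 11.4 | 11.2–11.4 |
| 75% | 11.2 | 11.1–11.2 |
| 100% | none | none |

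**5. Cost of losing one OSTT pair.** Paired t-test, two-sided 0.05, noncentral t, with the effects and SDs in section VII. HOMA-IR (1.8, SD 2.7): 80.7% at n = 20, which reproduces the stated 81%, and 78.5% at n = 19. Two-hour glucose (14.4, SD 14.4): 98.9% at n = 20, which agrees with the stated 99%, and about 98.4% at n = 19.

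**The case against.** The strongest reply is that no commitment is broken. The CBC is offered as an addition to volume guidelines, a weight floor, optional omission of stored blood and tracking of other studies. The protocol never promises to monitor haemoglobin, and 11 g/dL is an entry criterion, not a limit at Visit 5. That stands: this is a proposed improvement, and the screening-lab discontinuation rule is not at fault.

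The absence is also inferred from lists that are known to be incomplete. The OSTT Labs table omits C-peptide, which the Aim 2 methods say is sampled, and the baseline metabolic bloods are not itemised. A reader might infer that haemoglobin is definitely not measured at Visit 5. The documents do not go that far, although describing the CBC as a screening lab points that way.

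A reader might also infer that nothing in the plan could prompt a smaller draw. That is too strong: weight is measured at admission, 300 mL is a maximum, and stored blood may be omitted. Weight can prompt a smaller volume, but it cannot show that a girl has become anaemic. History and blood pressure at admission, and the investigator's review of abnormal results, act only on what is noticed or measured.

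Finally, Visit 3 also comes about 4 weeks or more after the only listed haemoglobin. True, but only the small screening sample separates the two, whereas Visit 5 follows a draw of up to 300 mL.

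**Conclusion.** The point holds as a minor participant-safety improvement. A check that the protocol itself counts as protection is not listed again before the second large draw, and the other protections do not replace it. It rests on reading the lab lists as showing no haemoglobin after screening; if one is already planned, a one-line clarification settles the matter.

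Two stronger readings are tempting and unsupported. The first is that girls will become anaemic: recovery over about 8 weeks is unknown, and with full recovery the number affected is none. The second is that the mL/kg figures measure this problem. They show that the weight cutoff does not achieve what the section says, but that is a separate error, and a haemoglobin result would not correct it.

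There is no effect on the primary endpoint, its sample size or its analysis.

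**What to change.** Add one rapid haemoglobin at Visit 5 to the Study Calendar and the OSTT Labs table, taken from the IV placed for the OSTT and resulted before OSTT sampling. Using that IV avoids an extra needle stick. The price is that the result arrives after the overnight deuterated water, which is taken "three times during the night with doses at 6-8PM, 10-11 PM and 2-3 AM"; testing before the first dose would probably need a separate stick.

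State the action. If the result is below 11 g/dL, first reduce the draw by omitting stored samples, as the Blood Sampling section already allows. Skip the OSTT only if that is not enough, and refer the girl for follow-up. Add to section VI.C that this does not count as being unable to complete study procedures, so she is not withdrawn and her Visit 4 MRI is kept. The screening-lab rule stays as it is.

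The cost is one small tube per girl, a short amendment and, occasionally, a shortened or missing second OSTT. One lost pair lowers power by about 2 percentage points for HOMA-IR and about half a point for 2-hour glucose; reducing the draw first should avoid most such losses. The volume statement and the 38 kg cutoff need their own correction.

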#### Inclusion Criteria:

- 1) Female
- 2) Ages 12-21
- 3) Sedentary- less than 2 hours of moderate (jogging, swimming etc) exercise a week.
- 4) BMI equal or greater than the 90th percentile for age and gender

5) PCOS per the most stringent NIH criteria adapted for adolescents (irregular menses >24 months post-menarche and clinical or biochemical hypertestosteronemia)

6) HS per FibroScan ultrasound, with CAP score of >225.

[figure not shown]

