#### Exclusion Criteria:

1. Use of medications known to affect insulin sensitivity: metformin, oral glucocorticoids within 10 days, atypical antipsychotics, immunosuppressant agents, HIV medications, hormonal contraception. Dermal patch or vaginal ring contraception methods.
2. Currently pregnant or breastfeeding women. Development of pregnancy during the study period will necessitate withdrawal from the study.
3. Severe illness requiring hospitalization within 60 days
4. Diabetes, defined as Hemoglobin A1C > 6.4%
5. BMI percentile less than the 90th percentile for age and sex. Weight >325 lbs or <84 lbs.
6. Anemia, defined as Hemoglobin < 11 mg/dL
7. Diagnosed major psychiatric or developmental disorder limiting informed consent
8. Implanted metal devices that are not compatible with MRI
9. Use of blood pressure medications
10. Known liver disease other than NAFLD or AST or ALT >125 IU/L

[figure not shown]

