Location of Visit	CHCO CTRC Outpatient	UCD Outpatient, Brain Imaging Center	CHCO or University Hospital Inpatient	UCD Outpatient, Brain Imaging Center	CHCO or University Hospital Inpatient

**Timeline:** The time between the initial screening visit and completion of the study will be less than 6 months. After confirmation of eligibility and randomization, participants will be on 4 weeks of EAA or placebo and then Phase I study visits will be completed (Visits 2 and 3). There will be approximately 4-

week washout period and then participants will crossover treatment, and complete another 4 weeks of EAA or placebo. Phase II study visits (Visits 4 and 5) will be completed.

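### The 38 kg weight floor does not keep a 300 mL OSTT draw within 5 mL/kg; that takes a body weight of 60 kg

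*Combined protocol and SAP*

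**What the plan says.** Under Blood Sampling (section III.D, item 1, the paragraph on minimizing risk), the routine Pediatric CTRC limits are 2.5 mL/kg for a single draw and "no more than 5 ml/kg over a 4 week period". The planned volume follows: "The OSTT visit includes up to 300 ml of blood which will occur within 4 weeks of the initial visit". From this the section concludes that the visit meets both an NIH limit of 9 mL/kg in 6–8 weeks and the hospital's "institutional guidelines of 5 ml/kg". It then names a safeguard: "We will use a minimum weight cutoff of 38 kg to remain below the most conservative pediatric CTRC blood drawing guidelines".

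The Exclusion Criteria carry the same floor in pounds: "Weight >325 lbs or <84 lbs". No other section sets a higher minimum weight or scales the OSTT volume to weight. The one provision for an individual participant is that "the blood planned to be frozen and held could also be omitted if needed to reduce blood volume for a particular participant".

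**The concern.** The section presents compliance with 5 mL/kg as settled and the 38 kg floor as the means of securing it. A fixed ceiling in millilitres meets a per-kilogram limit only above a certain weight, and for these figures that weight is well above 38 kg. A girl who satisfies every written criterion could therefore have more than 5 mL/kg drawn at one visit while the protocol says that this cannot happen. Staff who rely on the statement have no written reason to reduce the draw at, say, 50 kg. The stake is participant safety and the accuracy of what the ethics board was told, not the trial's inference.

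**Working it through.** **Inputs from the documents**
- OSTT volume: up to 300 mL (Blood Sampling)
- Limit: 5 mL/kg over 4 weeks (Blood Sampling)
- Weight floor: 38 kg (Blood Sampling); 84 lb × 0.4536 = 38.1 kg (Exclusion Criteria)
- Screening blood: 11.5 mL, and 25.5 mL for PCOS patients (Blood Sampling). The text does not make clear whether the second figure includes the first.

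**Can 38 kg be reproduced?** Minimum weight = volume / limit.
- At 5 mL/kg: 300/5 = 60.0 kg (132 lb)
- At 7 mL/kg, a volume the section mentions for other studies that give iron: 300/7 = 42.9 kg
- At 9 mL/kg (NIH): 300/9 = 33.3 kg; with screening blood, 325.5/9 = 36.2 kg or 337/9 = 37.4 kg

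The 38 kg floor is enough for 9 mL/kg. It is not enough for 7 or 5 mL/kg. The 2.5 mL/kg single-draw limit is left aside because OSTT sampling is serial.

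**Load at the floor.** 300/38 = 7.89 mL/kg, about 1.6 times the limit. The permitted volume is 5 × 38 = 190 mL, so the ceiling exceeds it by 300 − 190 = 110 mL.

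**If screening blood falls in the same 4 weeks**, the threshold rises:
- (300 + 11.5)/5 = 62.3 kg
- (300 + 25.5)/5 = 65.1 kg
- (300 + 11.5 + 25.5)/5 = 67.4 kg

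Whether it does is unclear. Blood Sampling puts the OSTT within 4 weeks of the initial visit, but the Timeline paragraph says "participants will be on 4 weeks of EAA or placebo and then Phase I study visits will be completed". On the Timeline reading the threshold stays at 60 kg.

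**Realistic size.** The documents give no weight distribution and no BMI cut-off in kg/m². As an assumption, take the lightest likely entrants at BMI 22–24 kg/m² and height 1.50–1.60 m. Weight = BMI × height²; cap = 5 × weight.

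| BMI | Height (m) | Weight (kg) | 300 mL as mL/kg | Cap (mL) | Excess (mL) |
|---|---|---|---|---|---|
| 22 | 1.50 | 49.5 | 6.06 | 247.5 | 52.5 |
| 24 | 1.50 | 54.0 | 5.56 | 270.0 | 30.0 |
| 22 | 1.60 | 56.3 | 5.33 | 281.6 | 18.4 |
| 24 | 1.60 | 61.4 | 4.88 | 307.2 | none |

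The largest excess in the table is 52.5/300 = 17.5% of the ceiling.

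**The case against.** The best defence is that the section is partly self-correcting. The 300 mL is a maximum, the 5 mL/kg rule it cites already scales with weight, and stored blood can be left out for an individual. Entry also requires BMI at or above the 90th percentile, steatosis on FibroScan and "irregular menses >24 months post-menarche", so light participants should be rare. The excess fades quickly with size: at 1.65 m, BMI 22 gives 22 × 1.65² = 59.9 kg, about 0.5 mL over. The 9 mL/kg NIH statement does hold at 38 kg for one OSTT visit, even with screening blood (325.5/38 = 8.57 mL/kg). Anaemia is an exclusion.

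Much of this stands as a limit on practical impact. It does not rescue the statement. An assurance has to hold at the maximum it authorises. Omitting stored blood is discretionary, has no weight trigger and no stated volume, and nothing shows that it would save 52 mL, let alone 110 mL. It is also not fully clear which tubes it covers: the Visit 3 description groups metabolomics samples with stored blood, whereas the OSTT Labs table lists them separately, and metabolomics is a secondary outcome. Meeting the looser NIH limit does not show that the institutional one is met, and anaemia screening does not limit volume.

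**Conclusion.** The concern holds. At the stated ceiling, 5 mL/kg requires 60 kg, and the 38 kg floor does not secure it. That result rests only on the protocol's own figures. The likely excess per affected girl, 0 to about 52 mL, rests on the assumed BMI and height and on the full 300 mL being drawn; actual draws may be smaller. The 110 mL excess at the floor is an unlikely extreme. The number of participants under 60 kg cannot be derived from the documents and is probably small. This should be fixed because it is a safety assurance covering minors.

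**What to change.** Replace the compliance sentence and the 38 kg sentence with a binding cap, for example:

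> OSTT blood volume will not exceed the lower of 300 mL and 5 mL/kg × body weight, less any study blood drawn in the previous 4 weeks. Stored blood is omitted first whenever this cap is below the planned volume.

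State the essential (non-stored) volume so that the cap can be checked for lighter girls. It would help, though it is not essential, to name the order of omission: tubes for future markers first, metabolomics samples last. While amending, check the 9 mL/kg NIH limit across both OSTT visits if they can fall within 8 weeks of each other.

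The cost is amendment text, an ethics notification and less stored blood from a few lighter girls. If the essential volume exceeds the cap (247.5 mL at 49.5 kg, 190 mL at 38 kg), the very lightest would also give fewer OSTT or metabolomics samples.
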